15.0 TOXICITIES/RISKS/SIDE EFFECTS

The treating investigator or qualified designee will assess each subject to evaluate for potential new or worsening AEs as specified in the Schedule of Assessments (see Section 10.0) and more frequently if clinically indicated. Adverse experiences will be graded and recorded throughout the study and during the follow-up period according to NCI CTCAE Version 5.0. Toxicities will be characterized in terms regarding seriousness, causality, toxicity grading, and action taken with regard to trial treatment.

ZW25 Monitoring and Management of Adverse Events

Infusion-related Reactions

Some patients treated with IV infusions of therapeutic drugs have experienced concurrent infusion-related reactions (see CTCAE Version 5.0). The signs and symptoms may vary and include for example, headache, fever, facial flushing, pruritus, myalgia, nausea, chest tightness, dyspnea, vomiting, erythema, abdominal discomfort, diaphoresis, shivers, lightheadedness, hypotension, palpitations, and somnolence. Anaphylaxis might occur at any time during an infusion.

While ZW25 is a fully humanized antibody, infusion reactions may occur. Infusion reactions consist of a symptom complex characterized by fever and chills, and may include nausea, vomiting, pain, headache, dizziness, dyspnea, hypotension, rash, and asthenia. Severe and potentially fatal reactions may include bronchospasm, anaphylaxis, angioedema, hypoxia, and severe hypotension. Infusion reactions may occur during or immediately following the initial infusion or at a later time point. While severe reactions usually occur during or immediate after infusion, onset and clinical course can be variable.

Prior to dosing with ZW25, all patients must receive prophylactic treatment for infusion reactions consistent with institutional standards that includes a corticosteroid. The

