HER2 targeted therapies have been associated with cardiotoxicity. Therefore, only patients who have baseline normal left ventricular ejection fraction and no history of significant cardiac disease will be eligible for treatment with ZW25. Patients with a lifetime cumulative dose of anthracycline >300 mg/m² or who have received anthracycline treatment within 90 days of the expected first dose of ZW25 are not eligible for treatment.

Patients are monitored per the study-specific protocol for changes in cardiac function. Cardiac monitoring includes assessment of ECG (frequency and type of abnormalities using standard 12-lead ECG, including heart rate, PR interval, QRS complex, QTcF), and echocardiogram (estimation of ejection fraction).

Management of decreased left ventricular ejection fraction (LVEF), regardless of relationship to study drug, is described in Table 3 below.

Table 3: Management Guidelines for LVEF Dysfunction

Left Ventricular Dysfunction	Management
Symptomatic cardiac heart failure	
• Discontinue ZW25
LVEF <40%	
• Do not administer ZW25• Repeat LVEF assessment within 4 weeks• If LVEF <40% is confirmed, discontinue ZW25
LVEF below institutional limits of normal and \geq 10% points below pre-treatment baseline	
• Do not administer ZW25• Repeat LVEF assessment within 4 weeks• If the LVEF has not recovered to within 10% points from baseline, discontinue ZW25
LVEF 40% to \leq 45% and decrease is $<$ 10% points from baseline	
• Continue treatment with ZW25• Repeat LVEF assessment within 4 weeks
LVEF $>$ 45%	
• Continue treatment with ZW25, as applicable

Gastrointestinal Toxicity

The most common ZW25-related gastrointestinal TEAEs ($>$ 20%) were diarrhea and nausea. Two patients in Part 1/2 developed ZW25-related Grade 3 diarrhea (20 mg/kg), which subsequently resolved with medications. No patients in Part 3 developed ZW25 Grade 3/4 gastrointestinal toxicity.

Table 4: Management Guidelines for Potential Infusion-related Reactions

Infusion Reaction CTCAE v5.0 Severity Grade	Management

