For any Grade 3 hepatic toxicity that does not resolve to baseline within 7 days, an abdominal CT scan must be performed to assess whether it is related to disease progression.

Re-treatment Criteria

To Begin a New Cycle of Treatment or continue treatment within a cycle

For a patient to begin a new cycle or continue a cycle of therapy, the following criteria must be met.

- ANC must be ≥ 1.0x10⁹/L (1,000/µL)
- Platelet count must be ≥ 75 x 10⁹/L (75,000/µL)

- All non-hematologic toxicities for which a causal association to study treatment cannot be ruled out, must be \leq Grade 1 (except alopecia) or returned to baseline.
- If the patient does not meet these criteria, dosing will be delayed and the patient should be re-evaluated within 48-72 hours. Dosing will resume if these criteria have been met.

If treatment is delayed due to treatment-related toxicity longer than one cycle, then the patient should be removed from study treatment. In such cases, continuation of study treatment may be considered for those patients who have experienced clinical benefit if agreed upon by the principal investigator and Zymeworks.

The use of granulocyte growth factors in accordance with ASCO guidelines may be implemented at the discretion of the treating physician.

Follow-up for AEs Leading to Discontinuation

Patients who discontinue study treatment for an AE or an abnormal laboratory value must be followed at least once a week for 4 weeks, and subsequently at 4-week intervals until resolution or stabilization of the adverse event or laboratory abnormality, whichever occurs first.

Dose Modification Guidelines

ZW25 Dose Reduction Following an AE

ZW25 dose may be reduced at the discretion of the Investigator after discussion with Zymeworks. Patients who develop adverse events requiring an interruption of ZW25 may resume treatment at a reduced dose level as shown in Table 6.

Table 6: ZW25 Dose Modification Guidelines

Regimen	If the patient was receiving ZW25 at:
Dose Level 1	20mg/kg intravenously (IV) every two weeks
Dose Level -1	15 mg/kg every two weeks
Dose Level -2	10 mg/kg every two weeks

**Reduction of the ZW25 dose below 10 mg/kg will not be permitted.*

Overdose and Medication Error

Overdose: There is no known treatment/antidote available for ZW25. Supportive measures should be instituted if an instance arises in which a patient suffers an overdose of any study drug.

Memorial Sloan Kettering Cancer Center
[name]
[name]

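### Table 3 says both withhold and continue ZW25 for an LVEF above 45% that is below the institutional limit and at least 10 points under baseline, and no row precedence is stated

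*Combined protocol and SAP*

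**What the plan says.** All references are to the combined protocol and SAP. Section 15.0, under Potential Cardiotoxicity, introduces the table by saying that management of a decreased LVEF, "regardless of relationship to study drug, is described in Table 3 below". Table 3 has five rows; three matter here.

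- **Row 3.** The condition opens "LVEF below institutional limits of normal and" adds a fall of at least 10 points from the pre-treatment baseline. The action is to withhold ZW25 and repeat the LVEF within 4 weeks. Then: "If the LVEF has not recovered to within 10% points from baseline, discontinue ZW25". The row has no upper bound on LVEF.
- **Row 4.** LVEF from 40% up to and including 45%, with a decrease of less than 10 points: continue, and repeat within 4 weeks.
- **Row 5.** LVEF above 45%: "Continue treatment with ZW25, as applicable". There is no condition on the fall or on the institutional limit, and the closing qualifier is not defined.

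Inclusion criterion 7 (Section 6.1) requires a screening LVEF of at least 50%. Section 15.0 adds that baseline LVEF must be normal. The cardiac event of special interest in Section 15.2.2 pairs a fall of at least 10 points with an absolute value under 50%. The calendar in Section 11.0 schedules an echocardiogram every 12 weeks.

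**The concern.** Rows 3 and 5 can both be true of one echocardiogram result, and their instructions are opposite: stop dosing and re-measure, or carry on. Row 4 shows how the table could have kept the rows apart, because its limit on the size of the decrease prevents any overlap with row 3. Row 5 has no such limit.

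The protocol names cardiotoxicity as a known risk of HER2-targeted therapy, and Table 3 is its specific rule for a fallen LVEF. Under row 3 the patient has a hold, a repeat measurement within 4 weeks and possibly discontinuation. Row 5 on its own asks for no repeat. Two investigators could treat the same result differently, each able to cite the table.

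**Working it through.** There is no planned figure to reproduce; this is a check of the table's logic.

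**Inputs.** Write v for the current LVEF, B for baseline and L for the institutional lower limit, all in percent.

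- Row 3 applies if v < L and B − v ≥ 10.
- Row 4 applies if 40 ≤ v ≤ 45 and B − v < 10.
- Row 5 applies if v > 45.
- Eligibility gives B ≥ 50.
- L is not stated anywhere in the documents, so it is an assumption.

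**Rows 3 and 4.** One needs B − v ≥ 10 and the other B − v < 10, so they never overlap.

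**Rows 3 and 5.** Both apply when 45 < v < L and B − v ≥ 10. In whole numbers the lowest such value is 46, so B must be at least 46 + 10 = 56. Eligible patients with a baseline of 50–55% cannot be in the overlap.

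| Assumed limit L | LVEF values meeting both rows | Baseline needed |
|---|---|---|
| 46 or lower | none | – |
| 47 | 46 | 56 or more |
| 48 | 46–47 | 56 or more for 46, 57 or more for 47 |
| 50 | 46–49 | 56 or more for 46, rising to 59 or more for 49 |

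**Example, L = 50, B = 60, v = 48.** The fall is 60 − 48 = 12, which is at least 10, and 48 < 50, so row 3 applies: withhold. Also 48 > 45, so row 5 applies: continue. Row 4 does not apply, because 48 exceeds 45.

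**Contrast, L = 50, B = 57, v = 48.** The fall is 57 − 48 = 9, so row 3 does not apply and only row 5 does.

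**Why L near 50 is plausible.** The entry criterion (at least 50%), the requirement that baseline be normal, and the under-50% threshold for the event of special interest all point that way. None of them defines the institutional limit.

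**Does other text settle it?**

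- The opening of Section 15.0 allows assessment "more frequently if clinically indicated". That permits an earlier look but does not choose a row.
- The re-treatment criteria begin "All non-hematologic toxicities for which a causal association to study treatment cannot be ruled out, must be" and go on to require Grade 1 or lower, or return to baseline. They could stop dosing, but only for toxicity possibly related to treatment, whereas Table 3 applies whatever the cause. Whether these LVEF values exceed Grade 1 depends on CTCAE grading, which the documents do not reproduce.
- Section 12.0 (treatment-related events) and the paragraph on other non-hematological toxicities in Section 15.0 require discontinuation for cardiac events of Grade 3 or higher. Whether the overlap values reach Grade 3 again depends on CTCAE.
- Section 15.2.2 governs reporting, not dosing.

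**Separate minor point.** The infusion-reaction text in Section 15.0 says to interrupt the infusion when a reaction occurs. Table 4 keeps the rate unchanged for a Grade 1 reaction unless it worsens.

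**The case against.** The strongest reply is that row 5 is a residual row. The table runs from most to least severe, row 3 is a specific two-part rule with an explicit hold, and row 5 is the broadest row and the only one with a loose qualifier. Row 5 also has a sensible residual role: with a limit of 50%, an asymptomatic fall from 70% to 58% meets no other row. This is a natural reading and it lowers the severity. It does not remove the point, because the protocol neither states it nor defines the qualifier.

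A second reply is that the overlap depends on a limit the documents do not give. That stands, and the size is conditional for that reason.

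Four stronger readings are tempting but not supported:

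- **Six doses before the next echocardiogram** (12 weeks ÷ 2-week dosing = 6). This requires row 3 to be ignored entirely, with no earlier assessment and no re-treatment check intervening. It is a hypothetical ceiling, not an expected consequence.
- **A wider band from a limit above 50%** (for example 46–54% at 55%). Such limits fit poorly with entry at 50% combined with the requirement of a normal baseline.
- **A conflict between row 1 ("Symptomatic cardiac heart failure") and row 5.** They overlap only on the most literal reading. Row 1 discontinues without condition, and the Grade 3 or higher cardiac rule may also apply, so this is marginal.
- **A conflict between rows 2 and 3.** Both withhold and repeat within 4 weeks. Row 2 ends treatment if a value under 40% "is confirmed, discontinue ZW25"; row 3 has a different trigger. Both triggers can be applied together, so these rows are compatible.

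**Conclusion.** The point holds for rows 3 and 5: as written, Table 3 gives opposite dosing instructions for one LVEF state, and no visible text resolves them. At an assumed limit of 50%, that state is LVEF 46–49% with a baseline of at least 56% and a fall of at least 10 points. At a limit of 46% or lower there is no whole-number overlap.

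The text available for review gives no LVEF event rate, so the number affected among the 25 planned patients is unknown. The response-rate endpoint, the two-stage design and the sample size are not affected. Because row 5 is quite likely intended as residual, this is a should-fix reconciliation of wording. A reader might infer that the protocol directs continued dosing despite a marked LVEF fall; it does not, since row 3 says the opposite for the same state. The Grade 1 infusion-reaction mismatch is real but minor and adds no weight here.

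**What to change.** Reconcile rows 3 and 5 of Table 3 so that each LVEF state carries one instruction, or add a sentence stating which row governs when more than one applies. The choice belongs to the sponsor's clinical team; this review does not suggest which instruction is right. Giving the institutional limit as a number would help but is optional.

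Separately, reconcile the infusion-reaction text in Section 15.0 with the Grade 1 row of Table 4.

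The cost is a wording clarification to one table and one sentence on infusion reactions. Sample size, endpoints, analyses and visit schedule do not change.

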ZW25 will be administered by IV infusion in 0.9% normal saline over 120 to 150 minutes. If for a particular patient the first 2 doses administered are well tolerated, the infusion duration for that patient may be decreased to 90 minutes. If the next 2 doses are well tolerated, the infusion duration may be decreased to 60 minutes. **However, the infusion rate should not exceed 250 mL of 0.9% normal saline/hour** (Example: If a dose of ZW25 is diluted into 250 mL bag of saline, the infusion should be administered over at least 60 minutes. If a dose of ZW25 is diluted into 500 mL bag, the infusion should be administered over at least 120 minutes.) The study drug dosage will be calculated based on patient weight at Screening. Dose will be recalculated only if there is a change in weight by 10% from the assessment at Cycle 1 Day 1. Please refer to the Pharmacy Manual for further instructions and or specific guidelines regarding the preparation and administration of ZW25.

All patients should receive pre-medication as prophylaxis for infusion reaction as described in **Required Therapy** section of the protocol.

Overdose

Any overdose or incorrect administration of ZW25 should be noted on the Study Drug Administration Electronic Case Report Form (eCRF). Adverse events associated with an overdose or incorrect administration of ZW25 should be recorded accordingly on the eCRF.

Required Therapy

Prior to dosing with ZW25, all patients should receive prophylactic treatment for infusion reactions that consists of acetaminophen orally, diphenhydramine (or equivalent) orally or IV, and a corticosteroid 30 to 60 minutes prior to infusion of ZW25. The dosage of these pre-medications may be determined by local institutional practice; however, the drug supplier's recommendations are acetaminophen 650 mg orally, diphenhydramine 50 mg orally or IV, and hydrocortisone 100 mg IV or dexamethasone 10 mg IV. All premedication administered should be documented for each infusion. If a patient cannot tolerate one or more of the premedication, please contact the Principal Investigator to discuss alternatives.

Permitted Therapy

Patients are permitted to use the following therapies during the study:

- Oral contraceptives
- Prophylactic or therapeutic anticoagulation therapy (such as warfarin at a stable dose or low-molecular-weight heparin)
- Inactivated influenza vaccinations
- Megestrol administered as an appetite stimulant
- Inhaled corticosteroids (e.g., budesonide)

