recommended regimen also includes acetaminophen orally, diphenhydramine (or equivalent) orally or IV 30 minutes through 60 minutes prior to infusion of ZW25 (recommended doses are: acetaminophen 650 mg, diphenhydramine 50 mg), and a corticosteroid (hydrocortisone, dexamethasone, or equivalent). If an alternative premedication regimen is thought to be required, approval from Zymeworks, Inc. should be sought. For patients who experience an infusion reaction despite initial premedication, additional prophylactic treatment may be added prior to subsequent doses, including an H2 blocker such as ranitidine as per institutional guidelines.

In the event of an infusion reaction, ZW25 infusion should be interrupted and medical therapy administered according to institutional standard of care (which, depending upon severity of the event, may include but not be limited to use of H1 and H2 inhibitors, corticosteroids, oxygen, IV fluids, epinephrine, and bronchodilators). Patients should be evaluated and carefully monitored until complete resolution of signs and symptoms. ZW25 should be discontinued in patients who experience a life-threatening (Grade 4) infusion reaction. Patients who experience a Grade 3 infusion reaction may be retreated at the discretion of the investigator at the next scheduled treatment. Such patients should receive additional prophylactic medication that may include a corticosteroid, and the duration of the infusion should be increased.

Infusions should be administered over 120 minutes through 150 minutes for the first 2 doses. If tolerated, infusion time may be reduced to 90 minutes for the next 2 doses, with reduction to 60 minutes for subsequent infusions at the discretion of the treating physician. Patients who experience a Grade 1 or Grade 2 infusion reaction may resume infusion of drug at a reduced infusion rate (30% through 50% slower than initial rate).

Samples will be collected from all treated patients for retrospective analysis to detect the presence of antibodies to ZW25 (i.e., ADA). In the event that an infusion reaction occurs or there is a suspicion of a hypersensitivity event, analysis of available samples collected to date for that patient may be performed.

Potential Cardiotoxicity

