Grade 1: Mild, transient reaction	Maintain infusion rate unless progression of symptoms to \geq Grade 2; if symptoms worsen, refer to guidelines below Promethazine (or equivalent) 150 mg PO per day for nausea (or equivalent) Diphenhydramine (or equivalent) 25-50 mg PO or IV prn Methylprednisolone 125 mg (or equivalent) IV prn

Infusion Reaction CTCAE v5.0 Severity Grade	Management
Grade 2: Moderate	
Interrupt infusion and disconnect infusion tubing from patient
 
Promethazine (or equivalent) 150 mg PO per day for nausea
 
Diphenhydramine (or equivalent) 25-50 mg PO or IV prn
 
Methylprednisolone 125 mg (or equivalent) IV PRN
 
After recovery from symptoms, resume the infusion at 50% of the previous rate and if no further symptoms appear, gradually increase rate until infusion is completed.
 
For subsequent dosing in future cycles, patients should be pre-medicated with dexamethasone (or equivalent) 8 mg PO BID the day prior to drug administration and acetaminophen (or equivalent) 650 mg PO and diphenhydramine (or equivalent) 25-50 mg PO 30-60 minutes prior to dosing.

Grade 3: Severe, prolonged reaction not rapidly responsive to symptomatic medication and/or brief interruption of infusion; recurrence of symptoms following initial improvement; hospitalization indicated for clinical sequelae	
Immediately stop infusion and disconnect infusion tubing from subject
 
Administer diphenhydramine (25-50 mg) IV (or equivalent)
 
Administer IV steroids (methylprednisolone (or equivalent) up to 0.5mg/kg Q 6h) to treat ongoing reaction and prevent recurrence
 
Administer bronchodilators (nebulized albuterol/salbutamol, 2.5-5 mg in 3 mL of saline or equivalent) as medically indicated
 
Administer normal saline as medically indicated
 
Administer epinephrine (0.2-0.5 mL of a 1:1000 dilution (0.2-0.5 mg) SQ or IM) as medically indicated. Epinephrine should only be used if all other treatment methods fail to manage the infusion-related reaction.
 
Advise patient to seek emergency treatment and notify investigator/clinic if the infusion-related symptoms recur after discharge from clinic.
 
Report as a serious adverse event

Grade 4: Life-threatening consequences, urgent intervention indicated	Management as for Grade 3 reaction and permanently discontinue study medication treatment

Monitoring and Management of Diarrhea Following the Administration of Study Treatment: ZW25-associated Diarrhea

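### Table 4 sets a per-dose methylprednisolone ceiling for Grade 3–4 infusion reactions that is below its own as-needed dose for Grades 1–2 at any weight under 250 kg, and does not say how the two combine when a reaction worsens

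*Combined protocol and SAP*

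**What the plan says.** Section 15.0, Table 4, gives management by CTCAE grade. The steroid entries are:

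- **Grade 1 (mild, transient):** "Methylprednisolone 125 mg (or equivalent) IV prn". The row keeps the infusion running and adds "if symptoms worsen, refer to guidelines below".
- **Grade 2 (moderate):** the same 125 mg as-needed dose. Neither row gives an interval or a maximum.
- **Grade 3 (severe):** "Administer IV steroids (methylprednisolone (or equivalent) up to 0.5mg/kg Q 6h) to treat ongoing reaction and prevent recurrence".
- **Grade 4 (life-threatening):** "Management as for Grade 3 reaction and permanently discontinue study medication treatment".

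The text on infusion-related reactions earlier in Section 15.0 says that "ZW25 infusion should be interrupted and medical therapy administered according to institutional standard of care". It allows treatment to vary with severity and names corticosteroids among the options, but gives no steroid dose for treating a reaction. It does not say whether the text or Table 4 prevails if they differ.

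**The concern.** The same drug appears in all four rows on two different bases: a fixed dose without a limit for the two lower grades, and a weight-based limit for the two higher grades. At ordinary body weights the limit for a severe or life-threatening reaction is well below the single dose listed for a mild one.

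The rows can also meet in one patient. Grade 1 sends a worsening patient down the table. The Grade 3 label includes reactions that have not settled promptly with symptomatic treatment and reactions that return after improving, so some patients reaching that row may already have been treated under a lower one. The table does not tell staff what the Grade 3 figure means for them.

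What is at stake is clear instruction during an acute safety event. Infusion-related reactions are an adverse event of special interest (Section 15.2.2). The primary endpoint, sample size and analysis are not affected.

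**Working it through.** The plan states no derived figure on this point, so there is none to reproduce. The check is arithmetic on the Table 4 entries.

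**Inputs**

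- Grades 1 and 2: 125 mg per dose, as needed (Table 4).
- Grades 3 and 4: at most 0.5 mg/kg every 6 hours (Table 4).
- Body weight: an assumption, shown from 40 to 150 kg. The documents give no weight distribution. Individual weight is recorded, because Section 5.1 says of ZW25 that "The study drug dosage will be calculated based on patient weight at Screening".

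**Formulas**

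- Per-dose ceiling = 0.5 mg/kg × weight.
- Doses in 24 hours = 24 / 6 = 4, so the implied 24-hour ceiling = 4 × 0.5 × weight = 2 mg/kg × weight.
- Weight at which the per-dose ceiling equals 125 mg = 125 / 0.5 = 250 kg.
- Weight at which the 24-hour ceiling equals 125 mg = 125 / 2 = 62.5 kg.

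**Results**

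| Assumed weight (kg) | Grade 3–4 per-dose ceiling (mg) | Ceiling as share of 125 mg | 125 mg ÷ ceiling | Implied 24-hour ceiling (mg) | Does one 125 mg dose exceed the 24-hour ceiling? |
|---|---|---|---|---|---|
| 40 | 20 | 16% | 6.25 | 80 | Yes |
| 50 | 25 | 20% | 5.0 | 100 | Yes |
| 70 | 35 | 28% | 3.6 | 140 | No |
| 100 | 50 | 40% | 2.5 | 200 | No |
| 150 | 75 | 60% | 1.7 | 300 | No |

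The per-dose direction is the same at every weight in the range. The 24-hour comparison changes direction at 62.5 kg. It sets one 125 mg dose against four Grade 3 doses. Total Grade 1–2 exposure cannot be compared either way, because the as-needed entry has no maximum.

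**Can the text resolve the table?** It gives no steroid treatment dose to check against. It also differs from the table elsewhere: it interrupts the infusion for an infusion reaction, while the Grade 1 row keeps it running. The two have not been aligned, so one cannot be used to interpret the other.

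**How often would the severe rows apply?** The adverse-event summary in the background section reports treatment-related infusion reactions in 40.3% of Phase 1 Parts 1 and 2 patients, but that covers all grades. The related Grade 3 or higher events it names are fatigue, diarrhea, arthralgia and hypophosphatemia. The updated data in Section 3.6 report infusion reactions in 34%, within a list described as all Grade 1 or 2. Neither place names a related Grade 3 or higher infusion reaction. That is not the same as a stated count of zero.

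**The case against.** The strongest defence is that the entries are different kinds of order. The lower rows give an as-needed dose, and the Grade 3 row gives a repeating regimen for a reaction that is continuing or might return. Read in sequence, as-needed dose first and 6-hourly dosing afterwards, they need not conflict. Nothing in the documents says that the per-dose steroid must rise with grade, and the Grade 3 row also escalates in other ways: immediate stopping, bronchodilators, saline and epinephrine. Table 4 is headed as guidelines, the text allows institutional standard of care, and Appendix B leaves medication for suspected anaphylaxis to the physician in charge.

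Much of this stands, and it rules out three stronger readings that a reader might infer:

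- *A patient who worsens has already exceeded the Grade 3 limit.* The documents do not support this. The 125 mg dose is as needed and may not have been given, a reaction may first present at Grade 3, the allowance recurs every 6 hours, and nothing says that earlier steroid counts toward it.
- *Staff would have to depart from the protocol in an emergency.* The text already allows institutional practice.
- *The problem would affect about 40% of patients.* That figure is for reactions of any grade.

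The sequential reading does not remove the point. It is possible but not stated, and it does not explain a lower per-dose ceiling for a reaction that first presents at Grade 3 or 4. The reference to institutional practice supplies no dose and no order of precedence.

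**Conclusion.** The point holds as an internal inconsistency and an omission in Table 4. The per-dose ceiling for Grades 3–4 is below the Grade 1–2 dose at any weight under 250 kg: 20% to 40% of it at assumed weights of 50 to 100 kg. One 125 mg dose exceeds the implied 24-hour Grade 3 total only below 62.5 kg. How the entries relate when a reaction worsens is not stated in the table or the text.

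The 24-hour figure assumes that all four 6-hourly doses are given at the ceiling, and the weights are illustrative. The severe rows are likely to apply uncommonly, which limits the expected impact. The correction should still be made, because the rows govern acute safety management and the change is small. No view is taken on which entry is right.

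**What to change.** Reconcile the steroid entries in the four rows of Table 4 with each other, with the source they were taken from, and with the infusion-reaction text in Section 15.0. State whether the Grade 3–4 entry replaces, adds to or includes steroid already given at a lower grade, and whether the table or the text prevails where they differ. The clinical team decides the figures.

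The cost is wording in one table and its accompanying text, plus a medical check. It adds no procedures, visits or patients.

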Appendix B: Anaphylaxis Precautions

EQUIPMENT NEEDED

- Tourniquet
- Oxygen
- Epinephrine for subcutaneous, intravenous, and/or endotracheal use in accordance with standard practice
- Antihistamines
- Corticosteroids
- Intravenous infusion solutions, tubing, catheters, and tape

PROCEDURES

In the event of a suspected anaphylactic reaction during study treatment infusion, the following procedures should be performed:

1. Stop the study treatment infusion.
2. Apply a tourniquet proximal to the injection site to slow systemic absorption of study treatment. Do not obstruct arterial flow in the limb.
3. Maintain an adequate airway.
4. Administer antihistamines, epinephrine, or other medications as required by patient status and directed by the physician in charge.
5. Continue to observe the patient and document observation.

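### Table 4 carries a last-resort condition on epinephrine from Grade 3 into Grade 4 infusion reactions, which the same table labels life-threatening and urgent

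*Combined protocol and SAP*

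**What the plan says.** Four places in the protocol bear on epinephrine for infusion reactions.

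- **Section 15.0, Table 4, Grade 3 row.** The label begins "Severe, prolonged reaction not rapidly responsive to symptomatic medication and/or brief interruption of infusion". Among the measures listed is "Administer epinephrine (0.2-0.5 mL of a 1:1000 dilution (0.2-0.5 mg) SQ or IM) as medically indicated". The next sentence restricts it: "Epinephrine should only be used if all other treatment methods fail to manage the infusion-related reaction".
- **Section 15.0, Table 4, Grade 4 row.** The label is "Life-threatening consequences, urgent intervention indicated". The whole instruction is "Management as for Grade 3 reaction and permanently discontinue study medication treatment".
- **Section 15.0, Infusion-related Reactions (text before the tables).** This defines the range of events: "Severe and potentially fatal reactions may include bronchospasm, anaphylaxis, angioedema, hypoxia, and severe hypotension". It says to interrupt the infusion and treat as the institution normally would. On the choice of measures it adds: "depending upon severity of the event, may include but not be limited to use of H1 and H2 inhibitors, corticosteroids, oxygen, IV fluids, epinephrine". The list ends with bronchodilators.
- **Appendix B, Anaphylaxis Precautions.** For a suspected anaphylactic reaction during infusion: "Administer antihistamines, epinephrine, or other medications as required by patient status and directed by the physician in charge".

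**The concern.** The Grade 4 row borrows the Grade 3 instructions whole, including the condition that epinephrine waits until everything else has failed. Nothing in the Grade 4 row lifts that condition. Read literally, the table puts epinephrine last in the reactions it describes as threatening life, and Section 15.0 counts anaphylaxis among severe infusion reactions.

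What is at stake is patient safety: a possible delay in giving epinephrine in a Grade 4 reaction. No estimate, error rate or decision rule of the trial depends on it.

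**Working it through.** The main check is textual, and the plan gives no figure to reproduce. A short calculation then bounds how often the Grade 4 row might be used.

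**1. Does the condition reach Grade 4?** Yes. The row's only content is the reference to Grade 3 management plus permanent discontinuation. It has no exception and no epinephrine sentence of its own.

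**2. Does the condition fit each grade?**
- *Grade 3:* partly. Much of that label describes a reaction in which symptomatic medication has already fallen short, so a later place for epinephrine is defensible.
- *Grade 4:* no. The other measures listed are IV diphenhydramine, IV steroid (up to 0.5 mg/kg every 6 hours), bronchodilators and saline. Waiting for all of these to fail conflicts with a label that calls for urgent intervention.

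**3. Does other text remove the condition?**

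| Text | Epinephrine | Last-resort condition | Stated to override Table 4 |
|---|---|---|---|
| Table 4, Grade 3 | As indicated, then restricted | Yes | n/a |
| Table 4, Grade 4 | By reference to Grade 3 | Yes, by reference | n/a |
| Section 15.0, general text | Listed, not ranked | No | No |
| Appendix B | As patient status requires | No | No |

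The last two texts are permissive. They set no opposing order, but they do not lift the condition either, and Table 4 points to neither. Appendix B applies only where anaphylaxis is suspected.

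**4. How often might it matter?** The inputs are from Section 3.6, and phase 1 rates are assumed to carry over to this population.

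- *Any-grade infusion reactions:* 34% in the updated report and 40.3% in Parts 1 and 2. For 25 patients: 0.34 × 25 = 8.5 and 0.403 × 25 = 10.1. The updated report describes its treatment-related reactions as Grade 1 or 2, so these figures show only how often the table as a whole would be consulted.
- *Grade 4 infusion reactions:* the summary of Parts 1 and 2 says all Grade 3 or higher events were Grade 3 except an unrelated Grade 4 lung infection and an unrelated Grade 5 sudden death. That gives 0 of 67, and hence 0 of the 44 treated at 20 mg/kg every two weeks.
- *One-sided 95% exact upper limit with zero events:* 1 − 0.05^(1/n).
  - n = 67: 1 − 0.05^(1/67) = 0.0437, and 25 × 0.0437 = 1.1 patients.
  - n = 44: 1 − 0.05^(1/44) = 0.0658, and 25 × 0.0658 = 1.6 patients.

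The point estimate is zero. The limits reflect the size of the phase 1 sample and are not expected counts. The documents give no rate for anaphylaxis.

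**The case against.** The strongest reply is that the protocol already contains the right answer. Appendix B is the more specific text for suspected anaphylaxis and imposes no order. The general text in Section 15.0 refers every infusion reaction to institutional care according to severity, and this is a single-centre trial with one such standard. Table 4 is headed as guidelines, and the sentence before the restriction leaves epinephrine to medical indication. Bronchodilators and saline are also given only if indicated, so one may argue that they need not be tried first. On this view only Grade 4 reactions without suspected anaphylaxis are left, and when epinephrine belongs in those is a clinical judgement. None has been recorded in phase 1.

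Much of this stands as mitigation. Staff who follow the general text or Appendix B are not bound by the condition. That staff would turn first to the grade-specific table is a reasonable inference, but the documents do not state it. It is also fair to say that deleting the sentence changes Grade 3 guidance, where the condition partly fits.

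It does not remove the defect. No order of precedence is given, so a reader of Table 4 has no reason to set its explicit restriction aside. Diphenhydramine and IV steroid are listed without an indication qualifier, so even the lenient reading puts those two before epinephrine in Grade 4. The restriction also immediately narrows the sentence on medical indication, so the row pulls in two directions. Rarity lowers the likelihood of harm but does not make the rule right for the row it governs.

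**Conclusion.** The concern holds: as written, the instruction is wrong for Grade 4. The condition applies there by reference, conflicts with that row's own label, and is not lifted elsewhere in the protocol.

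The problem lies mainly in Grade 4, and the permissive texts soften it. No Grade 4 infusion reaction was recorded in 67 phase 1 patients, with upper limits of 4.4% (0/67) and 6.6% (0/44). Those limits assume that the phase 1 summary is complete and that its rates carry over. Part of the adverse-event subsection was not in the text available to me, so the zero count rests on the summary sentence in Section 3.6. The textual conclusion depends on none of these figures. The correction should be made on grounds of consequence, not frequency.

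**What to change.** Preferred: delete the last-resort sentence from the Grade 3 row. Epinephrine is then governed by medical indication in both grades, which still lets the physician hold it back in a Grade 3 reaction, and the Grade 4 row needs no further wording.

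Alternative, if the clinical team wants to keep the order for Grade 3: limit the sentence to Grade 3 reactions without suspected anaphylaxis, and state in the Grade 4 row that it does not apply there.

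In either case, add to Table 4 a cross-reference to Appendix B for suspected anaphylaxis, and keep Table 4's dose (0.2–0.5 mg) and its subcutaneous or intramuscular route. Appendix B should not become the governing text: it gives no dose, and its equipment list names subcutaneous, intravenous and endotracheal use but not intramuscular. The clinical team should confirm the final wording.

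The cost is one deleted sentence, or a short limit in two rows, plus one cross-reference. Visits, data collection, sample size and analysis do not change.
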